4. Compare results across the three care delivery sites and identify any patient-related variables that impact treatment success

3. Background

Since the introduction of the first DAAs to treat HCV about 2 years ago, there are compelling reasons for expanding access to treatment for all HCV patients including their safety and cost-effectiveness.¹ However, certain HCV populations such as the homeless and people who inject drugs (PWID) have a high prevalence of chronic HCV infection. At the same time these populations have significant barriers to accessing care and have low rates of treatment initiation for their HCV infection. The impact of highly potent and well-tolerated interferon-free HCV treatment regimens will remain negligible as long as access to therapy cannot be expanded to the most affected risk groups.

One strategy that addresses several barriers is co-localization or integrated care of HCV screening, evaluation, and treatment with other medical or social services. Co-localization has already been applied to settings with a high prevalence of HCV infection (e.g., correctional facilities and programs providing needle exchange, substance abuse treatment, and methadone maintenance) but is not uniformly available.

One of the major obstacles to HCV care in the homeless and PWID is the lack of treatment settings that are suitably adapted for the needs of this vulnerable population. Nevertheless, HCV treatment has been delivered successfully to PWID through various multidisciplinary models such as community-based clinics, substance abuse treatment clinics, and specialized hospital-based clinics. Models may be integrated in primary care--all under one roof in either addiction care units or general practitioner-based models--or can occur in secondary or tertiary care settings. Additional innovative models include directly observed therapy and peer-based models.
2,3,4

This current study uses a mixed care model approach where two unique safety net sites, one serving the homeless and the low income and the other, active injection drug users who utilize a needle exchange program, working in concert with a traditional gastroenterology/hepatology clinic to identify and treat HCV patients within their own care environment. A unique feature of this study is maintaining a real world setting for HCV treatment to occur. Allowing therapy to be given in an environment that is familiar and supportive should foster adherence and high rates of treatment success.

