This will be a prospective study at the two safety net clinic sites where 25 non-cirrhotic subjects at each site will receive HCV treatment with Zepatier. Patients will be followed by a care team comprised of a medical provider and pharmacist at each care site within their own medical home environment. Subjects will be monitored for treatment and lab adherence. Overall SVR 12 will be assessed for this study group. This SVR12 rate will be compared to the SVR12 rate of a retrospective cohort of 50 consecutive non-cirrhotic HCV patients treated in the Hepatology Clinic at Oregon Health and Science (OHSU) starting in 2015. A prospective cohort will not be necessary at OHSU, since SVR12 rates have been consistently within the range of what has been reported in the literature.

Study Definitions

Treatment failure -

- Primary treatment failure: detectable HCV RNA at week 12 post-treatment.
- Secondary treatment failure: despite achieving SVR12, detectable HCV RNA at 48-week follow-up posttreatment. This would suggest re-infection, if there is evidence of re-exposure to virus. In addition, repeat genotyping will be performed in order to determine if the genotype has changed from baseline. If so, this would also suggest re-infection.

Treatment discontinuation- therapy interrupted by either the subject due to compliance issues/side effects or by medical provider due to safety issues.

Reinfection- achieved SVR12, but at 48 weeks after completing HCV therapy HCV RNA is detected. If there is evidence of re-exposure to HCV infection and/or repeat genotyping demonstrates a different genotype from baseline genotype prior to starting HCV therapy.

Treatment Regimen Compliance -

- Medication Compliance- percentage of pills taken during 12-week therapy. Pill count is assessed at every clinic visit.
- Laboratory Compliance- percentage of completed scheduled lab draws
- Clinic Visit Compliance- percentage of attended scheduled clinic visits

5. Study Population

a. Number of Subjects

A total of 50 *retrospective* subjects will be enrolled at OHSU. Two separate prospective cohorts of 25 patients each will be enrolled at Old Town Clinic and Outside In, prospectively.

b. Inclusion and Exclusion Criteria

Prospective Study Cohort

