Consecutive clients/patients with documented chronic hepatitis infection (detectable HCV RNA) seen at one of the study sites that are interested in HCV treatment and fulfill inclusion/exclusion criteria will be enrolled. Each site will determine readiness for treatment. Final approval for treatment initiation and ongoing monitoring during treatment will be under the supervision of the medical provider panel led by [name].

Retrospective Study Cohort

The Electronic Medical Record of the OHSU hepatology clinic will be reviewed and patients treated for hepatitis C with Zepatier selected in a retrospective, sequential fashion, starting at the time of closure of enrollment at the two prospective sites.

Screening Data Disposition

All data collected during screening for patients not meeting inclusion criteria, or meeting exclusion criteria, will be destroyed immediately, EXCEPT for the reason for exclusion, which will be collected and saved in a de-identified manner until study completion for the purposes of establishing external validity.

Inclusion Criteria

- 1) Genotype 1b and genotype 1a without baseline NS5A resistance or Genotype 4
- 2) APRI Score <0.7; if >0.7 a Fibrosure/Fibrotest or Fibroscan score of F2 or less, plus no clinical or laboratory evidence of cirrhosis
- 3) Readiness for treatment based on ability to make >2/3 sequential office visits either prospectively or retrospectively.
- 4) Patients must be assessed to have decision-making capacity, be capable of consenting, and not be displaying evidence of overt intoxication.

Exclusion Criteria

- 1) Previously treatment for hepatitis C infection
- 2) Clinical, radiologic, or laboratory evidence of cirrhosis
- 3) Hepatocellular carcinoma, HIV or hepatitis B virus co-infection, elevated prothrombin time unrelated to anticoagulation, hemoglobin level less 11 g/dL, platelet count <150 × 10⁹ cells/L, WBC <4.0 x10³/mm³, aminotransferase levels more than 10 times the upper limit of normal, or albumin level <3.0 g/L, positive office-based pregnancy test.
- 4) Subjects taking medications that are contra-indicated to administer with Zepatier including phenytoin, carbamazepine, rifampin, St. John's Wort, and cyclosporine. Study pharmacists will assess drug interactions.
- 5) Persons under the age of 18

c. Vulnerable Populations

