After study completion, any future release of data collected will be contingent upon the repository guardian verifying a separate full IRB approval for each specific human subject research activity that uses identifiable repository data. The repository guardian will be personally responsible for verifying that future releases of data are done in concordance with pre-proposed limits and the original consent. Data transport at the time of any potential future IRB approved data sharing will be clarified and approved at the time of data by submission of an updated Repository Sharing Agreement and separate IRB approval. Any updated data requests and Repository Sharing Agreements will be stored alongside study data in the Red Cap repository in a separate file entitled "Repository Sharing Agreements and External Data Requests." This will be maintained and tracked by [name]. External researchers will be required to use the Red Cap repository for all data storage, therefore data transfer will not be necessary and data security ensured.

No data submittal from outside sources is expected.

8. Data Analysis

- 1) For primary endpoint: descriptive analysis and chi-squared test for comparative analysis
- 2) For secondary endpoints:
 - Descriptive analysis
 - Explore bivariate and multivariate associations between psychosocial factors computed through scales (e.g., stigma, social support, quality of life) and (a) treatment readiness at baseline, (b) treatment outcomes [SRV, biological outcomes, etc.] at 12 months, (c) re-infection (or SRV) at 48 months. Demographic controls will include age, education, work status, and relationship status.
 - Conduct constant comparative qualitative analysis of focus group and individual discussions using Atlas.ti software. The domains of analysis will include lived experiences with stigma, discrimination, positive and negative social support systems, and risk management. Emergent themes and domains identified through qualitative analysis will result in a richer understanding of factors that contribute to implementing successful treatment for people who currently use drugs.

In addition to the above, mixed methods data will comprise biological data, psychosocial data collected via questionnaires, and qualitative narrative data from transcribed in-depth interviews.

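### The only between-cohort analysis of SVR12 is a crude chi-squared test, with no adjustment or sensitivity analysis for patient differences between the non-randomised cohorts

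*Combined protocol and SAP*

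**What the plan says.** Section 8 (Data Analysis) gives the whole method for the primary endpoint as "descriptive analysis and chi-squared test for comparative analysis". No covariates, strata, matching, weighting or sensitivity analysis are attached to it.

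The same section does plan some modelling, but for another purpose: "Explore bivariate and multivariate associations between psychosocial factors computed through scales" and readiness, treatment outcome and re-infection. Its covariates are also listed: "Demographic controls will include age, education, work status, and relationship status". Cohort is not an exposure in that work, and no HCV variable is a control.

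The fourth aim in Section 2 is to "Compare results across the three care delivery sites and identify any patient-related variables that impact treatment success". No method in Section 8 joins the two halves of that aim.

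The comparator is described in two ways. Section 4 calls it a "retrospective cohort of 50 consecutive non-cirrhotic HCV patients treated in the Hepatology Clinic at Oregon Health and Science (OHSU) starting in 2015", with no drug named. Section 5b has "patients treated for hepatitis C with Zepatier selected in a retrospective, sequential fashion, starting at the time of closure of enrollment" at the prospective sites, and Section 5e repeats this. Section 4 also says "A prospective cohort will not be necessary at OHSU", because OHSU response rates have matched the literature. That explains why data are not collected prospectively. It does not address comparability of the patients.

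**The concern.** The two groups are different people, recruited in different ways at different clinics. A crude difference in SVR12 therefore mixes the care model with whatever else differs between the cohorts. Some of those differences, such as housing and drug use, are the point of the study and should stay unadjusted. Others are ordinary HCV and demographic prognosis: subtype, fibrosis, age and gender.

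The Purpose and Goal in Section 2 credit the clinics' services with maintaining cure rates and look to national use of such sites. An imbalance in prognosis could create a gap or hide one. The second is the more awkward, because similarity is the result the study hopes to report. With only a crude test planned, the report would have no pre-specified way to show whether this happened.

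**Working it through.** **1. The plan's own figure.** Section 8 (Power/Sample Size) states 80% power for a 20-point difference with 50 per group. Two-sided alpha of 0.05 is my assumption; the plan states none. Formula: z = [d√n − 1.96√(2p̄(1−p̄))] / √(p1(1−p1) + p2(1−p2)).
- 95% v 75%: (1.414 − 0.990)/0.485 = 0.876, power 0.809. The 80% reproduces.
- 95% v 70%, the rates written beside it: (1.768 − 1.053)/0.507 = 1.408, power 0.920.

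The mismatch is a separate matter. Both figures describe the crude test and say nothing about confounding.

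**2. Can existing modelling adjust the comparison?** No. Its predictors are questionnaire scales, and Section 6 schedules the questionnaires at Visits 1 and 10 of the prospective sites. Chart-selected OHSU patients will not have them.

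**3. What does restriction already control?** Aim 1 limits every setting, OHSU included, to genotype 1 or 4. Section 4 makes both groups non-cirrhotic. Sections 5b and 5e limit OHSU to Zepatier. The mix of 1a, 1b and 4, fibrosis below cirrhosis, age and gender remain free to differ. The other Section 5b criteria (no previous treatment, no 1a NS5A resistance, no HIV or HBV) follow both cohort descriptions without saying clearly that they bind OHSU. The Section 6 readiness rule, which requires primary care at one of the two safety-net sites, cannot apply there.

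**4. Illustrative bias with no setting effect.** Bias = effect of the factor × difference in its prevalence. Both inputs are assumptions. The 5-point effect is the width of the efficacy range in the Risks and Benefits section (97 − 92); 8 to 15 points are larger assumed values. Rejection rates are exact, for the uncorrected chi-squared test with 50 per group, comparator 95%, two-sided 0.05.

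| Effect (points) | Prevalence difference | Bias (points) | Chance of p < 0.05 |
|---|---|---|---|
| none | – | 0 | 4.3% |
| 5 | 0.30 | 1.5 | 5.5% |
| 8 | 0.30 | 2.4 | 7.0% |
| 5 | 0.50 | 2.5 | 7.2% |
| 10 | 0.40 | 4.0 | 11% |
| 15 | 0.50 | 7.5 | 26% |

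For scale, the 95% half-width at 95% v 95% is 1.96 × √(2 × 0.95 × 0.05/50) = 0.085, or 8.5 points. Every bias in the table is smaller than that.

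**5. Which adjustment is feasible?** Expected failures are 100 × 0.05 = 5 if both rates are 95%, 2.5 + 12.5 = 15 at 95% v 75%, and 2.5 + 15 = 17.5 at 95% v 70%. At an assumed 10 failures per parameter, an outcome regression supports one parameter or none. A model for cohort membership draws on the 50 v 50 split instead. Simulated overlap weighting (2,000 runs per row, four covariates, no setting effect, factor prevalence 20% in the comparator by assumption) gave:

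| Prevalence difference, effect | Crude bias | Weighted bias | SD, crude to weighted |
|---|---|---|---|
| 30, 8 | −2.3 | +0.1 | 5.3 to 5.8 |
| 40, 10 | −3.9 | +0.2 | 5.6 to 6.3 |
| 50, 15 | −7.5 | −0.1 | 6.4 to 7.4 |

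The SD ratios are 5.8/5.3 = 1.09, 6.3/5.6 = 1.13 and 7.4/6.4 = 1.16. Effective sample size stayed at about 33 to 41 per group. The simulation assumes the factor is measured and included in the weights.

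**The case against.** The strongest reply is that HCV case mix is the part of the problem the design restricts most. If the Section 5b list covers OHSU, the cohorts also share treatment history, resistance status and absence of co-infection. The larger differences would then be substance use, housing, selection for readiness, chart-based ascertainment and calendar time, which weighting on HCV variables does not touch. This stands, and it rules out reading any crude difference as mainly HCV case mix. It does not remove residual imbalance, and the conditional matters because the plan does not settle it.

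Second, the primary objective in Section 4 asks whether results are similar to those expected in a clinic with a different population. That is partly a benchmark, for which a crude rate is the right summary, and Section 5f calls the study a pilot. This also stands. A reader might infer that the plan reads the chi-squared result as a causal effect of setting. Only the Purpose and Goal lean that way, so the crude test should stay primary.

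Third, the documents support no particular prognostic effect or imbalance. That is correct: the table in the working is a range of assumptions.

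Fourth, weighting has limits of its own. A fibrosis stage need not exist for everyone, because APRI alone can satisfy Sections 5b and 6. Overlap weighting also gives less weight to the safety-net patients least like hepatology patients, who are the group of interest. Both points shape the fix.

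**Conclusion.** The gap is real and moderate. A non-randomised comparison has a crude test and no planned check on patient differences, and the modelling elsewhere in Section 8 cannot supply one. The size of any bias cannot be derived from the documents. Under the stated assumptions it is about 1.5 to 7.5 points, against an 8.5-point half-width, and the crude test would reject in about 5.5% to 26% of trials with no setting effect, against 4.3% with no difference.

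Two stronger conclusions are tempting. One is that case mix is uncontrolled and will drive the result; restriction on genotype, cirrhosis and drug argues against it. The other is that similarity should be claimed only when crude and adjusted results agree. Without a margin or a definition of agreement that rule cannot be applied, and with about 5 failures expected at 95% v 95%, a few patients could decide it.

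**What to change.** 1. State one OHSU cohort definition. Reconcile Section 4 with Sections 5b and 5e on start point, direction of selection and drug, and apply the same HCV eligibility criteria to OHSU as to the prospective sites.
2. Keep the crude SVR12 comparison as primary.
3. Add one pre-specified supportive analysis: the SVR12 risk difference with 95% interval after overlap weighting on age, gender, genotype/subtype and APRI. Use APRI rather than fibrosis stage, since it needs only baseline AST and platelets, both covered by the standard-of-care tests in Section 6. Leave housing and drug use out of the weights.
4. Tabulate balance before and after weighting, and report the crude and weighted estimates side by side.
5. Attribute a result to care setting only with the caveat that readiness selection, calendar time and other unmeasured differences remain.

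The cost is one analysis and a short list of baseline fields from OHSU charts. The plan does not currently list those fields, so their availability should be confirmed. The weighted interval will be roughly 10 to 20% wider, and its estimate applies to patients who resemble both cohorts.

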Another unique offering at OTC is fully integrated Alcohol and Drug treatment services within primary care. We offer level 1 outpatient treatment for individuals suffering from opioid use disorder and others who suffer from comorbid chronic pain and substance use disorders. We have a robust medication assisted treatment program housed within primary care. Specifically, we offer buprenorphine and longacting naltrexone in conjunction with mandatory group and individual counseling sessions. These patients are some of the most adherent of the OTC population because the A&D program requires this (i.e. twice weekly groups, weekly medication dispensing, etc.). This population (i.e. PWIDs or have a history of IVDU) is disproportionately affected by HCV, so having this recovery support will not only improve treatment adherence but will reduce the risk of HCV re-infection.

The overall goal of OTC's HCV treatment program is to improve the care of its patients suffering from chronic Hepatitis C virus and to standardize the screening, diagnosis, work-up, and treatment of this condition throughout OTC. Patient-centered design is at the core of the creation of this program. Patient and provider co-design, utilizing human-centered design principles and tools, has been central to its development.

Essential parts of OTC's program include referral by the primary care provider (PCP), initial office visit and assessment with an OTC HCV provider, weekly medication dispensing, bi-weekly clinical pharmacist visits, monthly lab monitoring, referral to medication assisted treatment or mental health services as indicated, and optional participation in education and peer support sessions. These sessions will be initially modeled after previously validated peer support groups for treatment with interferon-based regimens,^{3,5} and further refined through our iterative, human-centered design process. Patients who are recent (previous 12 months) or current injection drug users will be strongly encouraged, but not required, to meet weekly in groups of less than 12 individuals, facilitated by certified drug and alcohol counselors. Patients electing to attend HCV health education sessions will partake in a 1 hour, certified health educator-lead, interactive hepatitis C education session, focusing on medical and social aspects of the disease, adherence, and re-infection prevention. [Integrative HCV Treatment Model At Two Study Sites](#)

Outside In HCV Treatment Program

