Individual	Self-worth	Please tell me about experiences when you’ve been denied HCV treatment in the past? Do you feel that you deserve to be treated for HCV? What does having access to HCV treatment mean to you? Do you think that people who use drugs deserve treatment?

	Perceived treatment selfefficacy	Do you think you will be able to take the treatment as prescribed? What factors do you think will make it challenging for you?
	Risk Behaviors	What is your understanding of safer injection practices? What risk behaviors do you think put you at risk for Hep C (ex. Needle sharing, sharing cocaine straws, etc)? How often did you/do you use safer practices (eg. Needle exchange).
Household	Sexual Partner	How has your sexual partner shown to be supportive of your health? How has your sexual partner made it more difficult for you to be healthy? How does your sexual partner feel about your participation in this study?
	Family	How has your family shown to be supportive of your health? How has your sexual partner made it more difficult for you to be healthy? How does your family feel about your participation in this study?
	Household resources	Income/financial resources/housing stability/work and migration/household size/access to health care
	Life Events	Birth, deaths/funerals, employment changes/changes in relationships
Organizational	Clinical sites	Perception of hospitals; perception of CBOs; comparing perception of context of study sites
	Group	Participation in support groups
	membership	
	Social services	Access to other services in relation to HCV treatment (e.g., housing, recovery, ORT, needle exchange)
Community	HCV perceptions	HCV acceptances/stigma; experiences of discrimination; What do people in your community think about HCV?
	Community resources	Access to health and other social services, public transportation; CBOs
	Cultural Norms	Practices around pill/medication taking, cultural beliefs about doctors and medical providers (e.g., trust, conspiracy theories)
	Information flow and beliefs	Rumors/beliefs about clinical studies, HCV transmission, HCV treatment
		Influence of institutional belief systems (e.g., churches, recovery fellowship)
		Informal and formal social and community networks (e.g., drug use networks)

7. Data and Specimens a. Handling of Data and Specimens

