All data will be collected by the primary provider, site principle investigators, or site coordinators. This data will be disassociated with personal identifiers, re-associated with a nondescript study ID, and uploaded into OHSU-sanctioned confidential data management service such as RED Cap, on a daily basis.

We will collect basic demographical information, including age, gender, ethnicity, substance abuse disorder/drug of choice and current use status, and housing status. The primary outcome measured will be SVR at 24 weeks (12 weeks post-treatment). Secondary outcomes include adherence (% pills missed, per fill and total), relapse or ongoing injection drug use at 48 weeks, and re-infection or treatment failure at 48 weeks.

Data storage will be for a period of 5 years or less, unless formal permission requested of the OHSU IRB for extension. Subjects will be consented for indefinite data storage.

Please see uploaded data collection and consent forms.

b. Sharing of Results with Subjects

All personal, clinical information will be shared with subjects in accordance of the standard of care. This includes lab values (done at CLIA certified laboratories Quest and Labcorps), imaging results, and other aspects of routine hepatitis C treatment. Results of secondary measures, including survey data and indepth interviews, will not be shared directly with subjects. Subjects will be able to access the final publication(s) upon request.

c. Data and Specimen Banking

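### Three of the four named controls for the psychosocial-factor analysis have no stated data source, and clinic site is not pre-specified as a term or stratum, so pooled associations may be confounded by site

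*Combined protocol and SAP*

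**What the plan says.** Section 8 (Data Analysis, secondary endpoints) plans bivariate and multivariate associations between scale scores (stigma, social support, quality of life) and treatment readiness, treatment outcome and re-infection. It then fixes the adjustment: "Demographic controls will include age, education, work status, and relationship status". No model form is given and no site term is mentioned.

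Section 7a describes the data: "We will collect basic demographical information, including age, gender, ethnicity, substance abuse disorder/drug of choice and current use status, and housing status". It closes with "Please see uploaded data collection and consent forms"; those forms are not in the document.

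Section 6 touches on work and relationships only as in-depth interview topics: "Income/financial resources/housing stability/work and migration/household size/access to health care" under household resources and "Birth, deaths/funerals, employment changes/changes in relationships" under life events.

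The fourth aim in Section 2 is: "Compare results across the three care delivery sites and identify any patient-related variables that impact treatment success". Section 4 makes identifying patient factors the secondary objective and labels the questionnaire analysis exploratory.

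**The concern.** There are two separate problems.

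First, the variables to adjust for and the variables said to be collected barely overlap. An analyst working from this document would not know where education, work status or relationship status come from. Housing and current drug use are listed as collected but have no stated role in the model.

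Second, the analysis appears to pool two clinics that differ by design. In Section 5e, the Outside In telephone message tells callers that they need to be current injectors, while Old Town Clinic draws its list from medication-assisted treatment. Section 5d also describes different care: weekly dispensing and an integrated addiction programme at Old Town Clinic, and tailored weekly or bi-weekly dispensing with syringe-exchange referral at Outside In. If stigma, support or quality-of-life scores differ between these groups and outcomes do too, a scale can look like a predictor of cure when it only marks the clinic. Age, education, work status and relationship status would not reliably remove that. The secondary objective could then name the wrong factor.

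**Working it through.** **Step 1. Compare the lists.**

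| Variable | Control in Section 8 | Listed as collected in Section 7a | Elsewhere |
|---|---|---|---|
| Age | yes | yes | – |
| Education | yes | no | not named as a data item |
| Work status | yes | no | interview topic only |
| Relationship status | yes | no | interview topic only |
| Housing status | no | yes | interview topic |
| Current drug use | no | yes | Outside In recruitment message |
| Clinic site | no | known by design | fourth aim |

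Overlap: 1 of 4 controls.

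**Step 2. How a site difference passes into a pooled association.** The plan has no figure to reproduce here, and all inputs below except the 25 subjects per site (Section 4) are assumptions. Let SVR12 be *a* at Old Town Clinic and *b* at Outside In. Let a fraction *h* of subjects report high stigma at Old Town Clinic and 1 − *h* at Outside In, with no stigma effect inside either site. With equal site sizes:

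- SVR12 among high-stigma subjects = *h·a* + (1 − *h*)·*b*
- SVR12 among low-stigma subjects = (1 − *h*)·*a* + *h·b*

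For *a* = 0.95, *b* = 0.75, *h* = 0.30:

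- high: 0.3 × 0.95 + 0.7 × 0.75 = 0.81
- low: 0.7 × 0.95 + 0.3 × 0.75 = 0.89
- odds ratio: (0.81/0.19) / (0.89/0.11) = 0.53

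| *a* / *b* | High stigma by site | SVR12, high vs low | Gap (points) | Odds ratio |
|---|---|---|---|---|
| 95% / 75% | 20% / 80% | 79% vs 91% | 12 | 0.37 |
| 95% / 75% | 30% / 70% | 81% vs 89% | 8 | 0.53 |
| 95% / 75% | 40% / 60% | 83% vs 87% | 4 | 0.73 |
| 80% / 60% | 30% / 70% | 66% vs 74% | 8 | 0.68 |
| equal | any | equal | 0 | 1.00 |

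The 80%/60% row averages to the 70% SVR12 that the Power/Sample Size paragraph assumes for the safety net clinics. The 95%/75% rows average to 85%.

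**Step 3. How often this would mislead.** Simulating the three 95%/75% rows with 25 subjects per site and an uncorrected chi-squared test at two-sided 5%, the spurious association is significant in about 21.6%, 12.0% and 6.5% of trials, top to bottom. With equal site SVR12 the rate is about 5%.

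A second simulation used a continuous scale and a linear probability model (2,000 runs). The false-positive rate without a site term was 7.6–9.2% for site SVRs of 80%/60% and 12.0–21.6% for 90%/50%, with the scale mean shifted by 0.5–0.8 SD between sites. With a site term it stayed at 4.5–5.8%.

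**Step 4. How many terms the data support.** The questionnaires are scheduled only at the prospective visits, so N is taken as 50. At 70% SVR12, failures = 50 × 0.30 = 15.

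- Three scales + four controls: 15/7 = 2.1 failures per parameter.
- The same plus site, housing and current use (one parameter each): 15/10 = 1.5.
- One scale + site + age: 15/3 = 5.

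With the 10% attrition allowed for in Section 8 (N = 45), failures fall to 13.5 and the last figure to 4.5. At 95% SVR12 there would be only 50 × 0.05 = 2.5 failures, too few for any of these models.

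**The case against.** A reader might infer that the model cannot be fitted as written. The documents do not support that. The Section 7a list is introduced as a partial one and points to data forms outside the document. Section 6 refers to a questionnaire appendix that is also not supplied, and Section 7c mentions data sheets for all ten visits. The three items may be on those forms. What stands is that the document gives them no source.

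A reader might also infer that site has been excluded and that the results are confounded. Neither is shown. The sentence in Section 8 concerns demographic controls and does not close the list; site is not a demographic. The fourth aim mentions the sites and patient variables together. Bias needs both the scale and the outcome to differ by site, and the documents give neither difference. What stands is that site is not pre-specified.

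The remark about Old Town Clinic's treatment-programme patients, "These patients are some of the most adherent of the OTC population because the A&D program requires this", is tempting as proof of a between-site outcome difference. It compares them with other Old Town Clinic patients, not with Outside In, so it is not evidence of one. There is also common ground between the sites: Section 5c says all prospective subjects have a substance use disorder, the eligibility criteria are shared, and Old Town Clinic's programme also provides for recent or current injectors.

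Finally, the analysis is exploratory and no primary conclusion depends on it. In most of the simulated trials no false predictor reaches significance. That limits the weight of the point but does not remove it, since this analysis is the route to the stated secondary objective.

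**Conclusion.** The concern holds in a limited form. Three of four named controls are absent from the stated list of collected variables, and the lists should be reconciled against the forms. Site is the most evident design-level difference among the prospective subjects and should be pre-specified. Under the assumed inputs, omitting it produces spurious odds ratios between 0.37 and 0.73 and false-positive rates of roughly 6.5% to 22%, against a nominal 5%. If the sites have similar outcomes or similar scale scores, the problem disappears. These figures illustrate a possible bias; they do not estimate one in this trial. The point is worth correcting because the correction uses information already held, but it affects only an exploratory analysis.

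**What to change.** Replace the sentence on controls in Section 8 with text such as:

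> *Each psychosocial scale will be examined in a separate model, with clinic site as a term or stratum and adjustment for age. Education, work status and relationship status will be considered only if recorded at Visit 1.*

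Then check the Visit 1 form. If the three items are on it, add them to the Section 7a list. If not, drop them from Section 8 or add the items to the form. Even if recorded, they should not all enter one model with this few failures.

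Do not require current drug use as a further covariate. Going by the Outside In recruitment message it should be nearly constant there, so it overlaps heavily with site. If failures turn out far fewer than 15, report within-site descriptive results or use penalised estimation.

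Cost: one sentence in Section 8, at most three extra questions at Visit 1, and no extra subjects. The downside is one more parameter: with one scale and age, adding site takes failures per parameter from 15/2 = 7.5 to 15/3 = 5.
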